7.8. Concomitant Medications and Treatments

5-FU and some of its metabolites are converted principally by liver enzymes (carboxylesterase and cytidine deaminase and PyNPase in tumor tissues). At present, it is unknown whether this metabolism is likely to be influenced by other treatments or alcohol, which either induce or inhibit certain liver enzymes.

Laxatives: The use of drugs with laxative properties should be avoided.

7.9. Warnings and Precautions regarding specific agents used in this protocol

7.9.1 5-Fluorouracil:

Cardiovascular: Although uncommon, fluorouracil has been associated with chest pain, anginal attacks, ischemic electrocardiographic changes, myocardial infarction, cardiomyopathy, and very rarely, sudden death. Most commonly, these effects occur when the drug is administered as a continuous infusion and within several hours from the start of the infusion. Patients with pre-existing coronary artery disease (CAD) appear to be at greater risk; however, most reported cases are in those with no previous history of CAD.

Dermatologic: Contact dermatitis, Alopecia, dry skin, fissuring, hand-foot syndrome, nail changes, rash, photosensitivity, and vein pigmentation have been reported in patients receiving intravenous fluorouracil

Hematologic toxicity: primarily neutropenia, occurred significantly more often in patients receiving bolus injections (31% versus 4%, RR 0.14, p less than 0.0001). Anemia and thrombocytopenia occurred in less than 5% of all patients. agranulocytosis, anemia, epistaxis, pancytopenia, and thrombocytopenia have also been reported during treatment with intravenous 5-FU. Factors increasing the risk for hematologic toxicity included a poor performance status and fluorouracil administration by bolus injection, while increased age, female gender, and a good performance status significantly increased the risk for nonhematologic toxicities. In hand-foot syndrome, continuous administration of fluorouracil was an additional prognostic factor.

Gastrointestinal: Commonly occurring symptoms during IV fluorouracil therapy are stomatitis, esophagopharyngitis, nausea, vomiting, anorexia and diarrhea

Neurologic: Neurological effects reported with the administration of fluorouracil include confusion, disorientation, euphoria, nystagmus, headache, and acute cerebellar syndrome.

7.9.2 Irinotecan:

Bone Marrow Suppression: Virtually all phase I and II studies of irinotecan have reported neutropenia that may be dose limiting. Anemia and lymphocytopenia have been observed as well.

GI: Diarrhea- abdominal cramping, and diarrhea (early diarrhea) during or shortly after irinotecan administration; late diarrhea (diarrhea occurring more than 8 hours after irinotecan administration) as the dose-limiting toxicities (depending upon the schedule). Other commonly observed adverse events include nausea and vomiting, anorexia, abdominal cramping. Infrequent occurrences of mucositis or colitis (sometimes with gastrointestinal bleeding) have been observed.

Skin: alopecia, asthenia. irinotecan may cause local irritation at infusion sites. Extravasation necrosis of the skin has not been reported in US studies.

Constitutional: Dehydration has occurred as a consequence of diarrhea, particularly when associated with severe vomiting. Patients may have an acute syndrome of lacrimation, diaphoresis, this syndrome is thought to be cholinergically mediated.

Pulmonary: Sporadic cases of pulmonary toxicity, manifested as shortness of breath, nonproductive cough, and transient infiltrates on chest X-ray have been reported.

Renal: Occasionally, abnormalities of serum Creatinine have been observed.

8. STUDY OUTCOME MEASURES

8.1. Objective Response Rate (ORR)

Objective response of measurable disease will be in accordance with the criteria described in RECIST 1.1 guidelines (45)

Only measurable lesions which have not been irradiated will be used as indicator lesions. These must have a minimum size of at least one diameter of 10 mm for liver, soft tissue lesions, lung, skin and lymph node lesions.

In responding patients, the response must be confirmed at a minimum of 4 weeks.

8.2. Progression Free Survival (PFS)

PFS will be measured as the time from Study Day 1 to the time the patient is first recorded as having disease progression or death, whichever comes first.

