6.4. Assessment during Treatment

The following will be obtained at regular intervals during treatment:

- a. History and physical examination Day 1 of each cycle
- b. Vital signs and weight assessment will be obtained prior to day 1 and day 15, (within 2 days).
- c. Drug toxicity (Adverse Drug Events) will be assessed every two weeks (toxicities will be graded according to the NCI CTC version 4.0).
- d. Complete blood count and serum chemistries (electrolytes including magnesium, calcium, potassium, BUN, Creatinine, liver function tests) will be obtained within 48 hours prior to each treatment, days 1 and 15.
- e. CEA serum level every as a baseline and once every cycle.
- f. Imaging studies including but not limited to CT scans prior to treatment as a baseline and every 8 weeks (+/- 5 days).

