6.4.1 On-Study Follow-Up Assessment

The following will be obtained at the end of the study

- a. Adverse events/toxicities
- b. Monitor for inflammatory or infectious sequela in patients with severe dermatologic toxicities.
- c. Performance status
- d. Weight

- e. Vital signs (blood pressure, pulse rate, respiratory rate, temperature)
- f. Physical examination
- g. Reevaluation of extent of tumor (same imaging method)

6.4.2 After Study Assessment.

After completion of the study, electrolytes including magnesium, calcium, potassium will be followed every two weeks for the duration of 8 weeks after completion of panitumumab therapy.

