6.5. Schedule of Assessments and Procedures

	Screening/Baseline		Every Treatment Cycle ^a		End of Study Visit
Day of Cycle	Within 28 days prior to first dose	Within 7 days prior to first dose	1	15	
5-FU bolus then cont infusion (over 46 hours)			X	X	
Irinotecan			X	X	
Panitumumab*			X	X	
Informed Consent ^b	X				
Medical History		X			
Malignant Disease / Treatment History	X				
Demographic Data	X				
General Physical Examination ^e	X	X	X		X
Vital Signs, Height, Weight, ECOG Performance Status		X	X	X	X
CBC ^g	X	X	X ^f	X	X
Complete Metabolic Panel Creatinine Clearance #		X	X ^f		X
Magnesium, potassium ^g		X	X ^f	X	X
CEA		X	X ^f		X
Urinalysis		X	— as clinically indicated —		
PT (or INR) & PTT		X	— as clinically indicated —		
Serum B-HCG ^c		X	— as clinically indicated —		
Tumor measurements (CT Scan)	X		Tumor measurements to be done after every 8 weeks of therapy		X
ECG	X		— as clinically indicated —		X

Adverse Events	X		— recorded throughout study	X
Concomitant Diseases & Treatment	X		— any changes noted throughout study —	X
KRAS and NRAS mutation testing ^d	X			

#Creatinine clearance is only required for baseline labs

*Minocycline will be given prophylactically for all patients starting the day prior to starting panitumumab and continue throughout the treatment duration (Please refer to section 6.2 for more details)

- a Each cycle is 28 Days, then repeated. Clinic visits can be performed +/- 2 days of treatment.
- b Informed consent must be obtained prior to any study-specific procedure
- c Only in women of childbearing potential
- d Archived tumor samples may be sent when they can be obtained at any time after screening process is started. May already completed prior to 21 days of enrollment.
- e Day 1 Cycle 1 is a chemotherapy only appointment. Clinic visit with physician is permitted but not mandatory
- f Day 1 Cycle 1 does not require labs to be repeated
- g Only CBC, magnesium and potassium to be obtained on day 15
- h MRI permitted with approval from PI
- i Survival data will be collected after the 8 week study assessment follow-up via chart review and/or phone follow-up every 3 months.

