6.8. Premature Withdrawal**

Should a patient decide to withdraw, all efforts will be made to complete and report the observations as thoroughly as possible.

1. Disease progression
2. Patient is unable to tolerate the toxicity resulting from the study treatment, even with optimal supportive care, in the opinion of the Treating Physician.
3. If retreatment must be held for > 6 weeks or at the discretion of the investigator (excluding the rest week).
4. Intercurrent illness that would, in the judgment of the Investigator, affect assessment of clinical status to a significant degree or require discontinuation of study treatment
5. Nonprotocol chemotherapy or immunotherapy is administered during the study
6. Noncompliance with protocol treatment
7. Patient becomes pregnant
8. Patient is lost to follow-up
9. Patient refuses to continue treatment (patient will continue to be followed for disease-free survival and overall survival)

**Patients have the right to withdraw from the study at any time for any reason. The investigator also has the right to withdraw patients from the study in the event of intercurrent illness, adverse events, treatment failure, protocol violations, administrative reasons or other reasons.

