7.4. Dose Adjustment for 5FU and Irinotecan Toxicities

A cycle is 4 weeks – with treatment on days 1 and 15. We do not make up day #15 treatments if a patient should require adjustment or omission based on outlined criteria below.

- This study will take into consideration previous toxicities experienced with FOLFIRI prior to enrollment. The initial dose of FOLFIRI will be determined by the investigator at time of trial initiation. Prior to enrollment, if the patient experienced significant toxicity with FOLFIRI and dose adjustments were required, these dose adjustments will continue upon initiation of this trial.
- For toxicities which are considered by the investigator unlikely to develop into serious or life-threatening events (e.g. alopecia, altered taste etc.), treatment will be continued at the same dose without reduction or interruption. In addition, no dose reductions or interruptions will be required for anemia as it can be satisfactorily managed by transfusions.
- For any event that is apparent at baseline, the dose modifications will apply according to the corresponding shift in toxicity grade, if the investigator feels it is appropriate. (e.g. if a patient has grade 1 asthenia at baseline which increases to grade 2 during treatment, this will be considered as a shift of 1 grade and treated as a grade 1 toxicity for dose modification purposes).
- If on the first day of chemotherapy treatment, the granulocyte count (ANC) is < 1,500 or the platelet count is < 75,000, treatment will be held for up to three weeks until ANC is ≥ 1200 and platelet count is ≥ 75,000. CBC should be obtained at least weekly when treatment is held. Chemotherapy doses will not be reduced based on nadir counts except in febrile neutropenia as defined below.
- If the dose is modified to manage an adverse event, it is recommended that the patient be seen by the investigator prior to re-starting study drug.
- If a rest period is extended due to toxicity, the "complete" cycle should be given afterwards with chemotherapy and panitumumab. If toxicity requires a dosing delay/interruption of both 5-FU and irinotecan of more than six weeks or at the

discretion of the investigator, the patient will be withdrawn from the study for toxicity reasons.

Table 1: Dose modifications during a course of therapy (day #15 of each cycle).

- Dose adjustments for hematological toxicity during a course of therapy are based on the blood counts obtained in preparation for that day of treatment.

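### A patient taken off for toxicity while progression-free has no scheduled disease follow-up after one exit scan, and with no PFS censoring date the event can fall at death; the bias favors the regimen but is probably small

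*Combined protocol and SAP*

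**What the plan says.** **Endpoint.** Section 8.2 measures PFS from Study Day 1 until the patient is "first recorded as having disease progression or death, whichever comes first". It gives no date for patients who have neither event. Section 10.2 names the Kaplan-Meier estimator and a Brookmeyer-Crowley interval and gives no censoring rule. Section 8.3, by contrast, gives overall survival a last-known-alive date.

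**Leaving without progression.** Section 6.8 item 2 reads "Patient is unable to tolerate the toxicity resulting from the study treatment", and item 3 covers treatment held for more than six weeks. Under section 7.4, after a delay of both chemotherapy drugs beyond six weeks or at the "discretion of the investigator, the patient will be withdrawn from the study for toxicity reasons".

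**Imaging.** Section 6.4 opens with "The following will be obtained at regular intervals during treatment" and lists "Imaging studies including but not limited to CT scans prior to treatment as a baseline and every 8 weeks (+/- 5 days"). The table in section 6.5 says "Tumor measurements to be done after every 8 weeks of therapy". Section 6.6 adds one tumor assessment within two weeks of withdrawal or discontinuation.

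**After exit.** Section 6.4.2 says "After completion of the study, electrolytes including magnesium, calcium, potassium will be followed every two weeks". Note i to section 6.5 collects survival every three months by chart review or phone. Only item 9 of section 6.8 keeps a withdrawn patient in disease follow-up: "Patient refuses to continue treatment (patient will continue to be followed for disease-free survival and overall survival"). It sets no scan schedule and names disease-free survival, which is not an endpoint of this trial.

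**The concern.** For a patient withdrawn for toxicity without progression, the search for progression stops at the exit scan while the search for death continues. Section 8.2 counts whichever is recorded first. Unless routine care happens to supply a progression date, the first recorded event is then the death, so the time from true progression to death is added to PFS.

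This is the primary endpoint of a 25-patient single-arm trial judged against a 4-month historical median. No concurrent arm shares the distortion, and its direction is always toward the regimen. The sample size in section 10.1 also assumes no loss to follow-up, which the assessment schedule does not secure for progression. Because no rule is written, the choice between counting the death and censoring at the exit scan could be made after the data are seen.

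**Working it through.** The plan has no figure of its own on this point, so the check starts from its design values and adds labeled assumptions.

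**From section 10.1:** n = 25; 2 patients per month, so 12.5 months of accrual; 6 further months of follow-up; exponential PFS; medians 4 and 6 months; one-sided alpha 0.10.

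**Assumed, because the documents do not say:** 2%, 5% or 10% of patients leave progression-free (0.5, 1.25 or 2.5 of 25); exit time uniform from 1 to 5.5 months; median survival after progression 6 or 12 months; hazard unchanged after exit. The nearest documented figures are for monotherapy (section 1.2.1.6): 2% of wild-type KRAS patients withdrew for panitumumab-related events, and 3% of all patients stopped for skin toxicity. The plan names an interval and no decision rule, so I take success to mean that the one-sided 90% Brookmeyer-Crowley lower limit exceeds 4 months: (S(4) − 0.5)/SE > 1.2816, with Greenwood's SE.

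**Step 1, everyone followed.** All patients have at least 6 months of follow-up, so S(4) is a simple proportion.
- 16/25: SE = √(0.64 × 0.36/25) = 0.096, and 0.14/0.096 = 1.46, which passes.
- 15/25: SE = √(0.60 × 0.40/25) = 0.098, and 0.10/0.098 = 1.02, which fails.
- Type I error at a true median of 4 = P(Bin(25, 0.5) ≥ 16) = 0.115.

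**Step 2, event counted only at death.** With λ = ln 2/4 = 0.1733:
- Chance of being progression-free at a uniform exit time: (e^(−λ) − e^(−5.5λ))/(4.5λ) = (0.841 − 0.386)/0.780 = 0.584.
- Chance of exiting progression-free before month 4 and then progressing before month 4: [(0.841 − 0.5)/0.1733 − 3 × 0.5]/4.5 = 0.104.
- Rise in apparent S(4) per unit share leaving: 0.104/0.584 = 0.178. This ignores deaths before month 4, so it is an upper bound.

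| Leave progression-free | Apparent S(4) | P(Bin ≥ 16), upper bound | Simulated, death only |
|---|---|---|---|
| 2% | 0.5036 | 0.122 | 0.121 |
| 5% | 0.5089 | 0.133 | 0.131-0.132 |
| 10% | 0.5178 | 0.153 | 0.147-0.151 |

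The simulation (200,000 trials per setting) allows for early deaths and agrees with the closed form.

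**Step 3, half of the missed progressions recorded from routine care.** Simulated type I error is about 12% at 2-5% leaving and about 13% at 10%.

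**Step 4, estimated median at a true 6 months, death only:** 6.08-6.09 (2%), 6.21-6.24 (5%), 6.45-6.51 (10%).

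**Step 5, censoring at exit instead.** Expected events at median 4 with full follow-up: 25 × [1 − (e^(−6λ) − e^(−18.5λ))/(12.5λ)] = 25 × [1 − (0.3536 − 0.0405)/2.166] = 21.39. With censoring at exit the simulation gives 21.01, 20.44 and 19.51, a loss of 0.38, 0.95 and 1.88 events. Type I error stays at 0.115-0.119. If the hazard after exit were 1.5 times higher, the true median at 10% leaving would be 5.84 months and the censored estimate 6.00, so censoring alone would be mildly optimistic.

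**The case against.** The biased result needs three things together: a patient leaves progression-free for toxicity, nobody records the later progression, and the analyst does not censor. Each can fail. Section 8.2 does not confine recorded progression to protocol scans. Note i already sends staff to the chart every three months. Section 1.3 foresees FOLFOX as the next line, so restaging is plausible. Kaplan-Meier implies some censoring. Section 6.8 also promises full effort to complete observations when a patient decides to withdraw, which with item 9 covers those who choose to stop.

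The group may be small, too. Section 7.5 stops panitumumab for intolerance without withdrawing the patient from the study. Entrants have already received FOLFIRI, and those who needed reductions above 50% are excluded. All of this stands, and it is why the effect is rated small. It does not close the gap: note i asks only for survival, and item 9 does not reach investigator-driven toxicity withdrawals.

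Section 6.6 asks for assessments every 8 weeks after the first, which might be read as open-ended. That sentence runs to the end of the study, however, and the separate exit assessment would be unnecessary if scanning continued.

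A reader might infer that type I error doubles. An exponential test does give 20.4-24.9% at 10% leaving with no progression captured, against 8.4% with full follow-up. But the plan names no such test, the documents give no source for 10%, and zero capture is the worst case. At 2% leaving, the same test gives 10.4-11.1%, near the planned 10%.

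**Conclusion.** The gap is real. The imaging schedule and the PFS definition, taken together, lean toward the regimen for toxicity withdrawals, and no censoring rule corrects this. With the plan's interval, type I error moves from 11.5% to about 12-13% at 2-5% leaving and about 15% at 10%, less if routine-care progressions are recorded. The estimated median rises by about 0.1-0.2 months at 2-5% and about 0.5 months at 10%. The leaving rates, exit times and post-progression survival are assumptions.

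Two stronger conclusions are not supported. The documents do not say that deaths will be counted this way; they leave it open, and the literal wording allows it. Nor do they show that off-treatment CTs must be mandated: at 10% leaving, CTs every 8 weeks until new therapy raise expected events from 19.51 to 20.08 (new therapy 1.5 months after exit) or 20.51 (3 months), a gain of 0.6 to 1.0. The point should be fixed because it touches the primary endpoint and the remedy is cheap. It does not invalidate the design.

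**What to change.** 1. **Sections 6.8 and 6.5.** Extend item 9's follow-up, reworded as progression-free survival, to every patient who stops without progression. Have the 3-monthly chart review in note i also record progression from routine-care restaging scans, including the last scan before any new therapy.
2. **Sections 8.2 and 10.2.** State that progression or death is an event on or off treatment while progression is still being ascertained, and that patients without such an event are censored at the last tumor assessment. A death after ascertainment has stopped is then not the PFS event. The text should define when ascertainment counts as stopped.

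The first change matters even with the second in place, because censoring alone is mildly optimistic if progression is faster off treatment.

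**Cost.** One protocol amendment, a little more data abstraction, no added patients. If every such patient ends up censored at exit, about 0.4 to 1.9 of 21.4 expected events are lost; recorded routine-care progressions recover part of that. Protocol-mandated CTs after exit, and a sensitivity analysis counting toxicity withdrawal followed by new therapy as an event, are optional.

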8.3. Overall Survival (OS)

Survival will be recorded as the time from Study Day 1 to the date of death or the last date the patient was known to be alive.

8.4. Duration of Response

Duration of response is defined as the date of first response to the date of first disease

progression or death due to any cause, whichever comes earlier, in the subset of subjects with confirmed objective response (RECIST criteria in Appendix 5).

9. SAFETY PARAMETERS

9.1. Abnormal Laboratory Test Values

In the event of unexplained abnormal laboratory test values, the tests should be repeated immediately and followed up until they have returned to the normal range and/or an adequate explanation of the abnormality is found.

9.2. Pregnancy

The patient will be removed from the study if she becomes pregnant during the study and immediately inform the investigator. The investigator should counsel the patient, and discuss the risk of continuing with the pregnancy and the possible effects on the fetus. Monitoring of the patient should continue until conclusion of the pregnancy.

Pregnancy occurring in the partner of a patient participating in the study must also be treated as described above.

9.3. Data Safety Monitoring and Submission:

Data Safety Monitoring Plan

The data and safety monitoring plan will involve the continuous evaluation of safety, data quality and data timeliness. Investigators will conduct continuous review of data and patient safety at their regular Disease Group meetings (at least monthly) and the discussion will be documented in the minutes. The PI of the trial will review toxicities and responses of the trial, where applicable, at these disease centered meetings and determine if the risk/benefit ratio of the trial changes.

Frequency and severity of adverse events will be reviewed by the PI and compared to what is known about the agent/device from other sources, including published literature, scientific meetings and discussions with sponsors, to determine if the trial should be terminated before completion. Serious adverse events and responses will be reviewed by the OSUCCC Data and Safety Monitoring Committee (DSMC). The PI will also submit a progress report (biannually for Phase II and quarterly for Phase I) that will be reviewed by the committee per the IRB of record as per the policies of the IRB.

Mandatory safety and trial review teleconferences will be scheduled and moderated by the Multi-Center Trial Program (MCTP). All sites involved in the study are expected to have a representative present for every call to review and discuss patients on study and other applicable agenda items. Meeting minutes will be used to document each teleconference. The minutes will be stored in the MCTP protocol files.

Data Submission

The study will be managed per the Multi-Center Trial Program (MCTP) policies. Subsite data must be submitted to the MCTP within 2 weeks of completion of each cycle. Data will be submitted using case report forms and the Data Submission Form cover sheet (refer to Supplemental Forms Document) supplied by the MCTP. Access to the OSU OnCore database may be provided to external participating sites for direct electronic data entry. All data submitted must be accompanied by supporting source documents.

Adverse Events

An adverse event is defined in the International Conference on Harmonization (ICH) Guideline for Good Clinical Practice as “any untoward medical occurrence in a patient or clinical investigation subject administered a pharmaceutical product and that does not necessarily have a causal relationship with this treatment.” (ICH E6:1.2). The ongoing review of safety data will include review of clinical AEs and SAEs including skin-related toxicity assessment and laboratory studies. The CTCAE version 4.0 will be used to grade all AEs, except panitumumab-related skin toxicity, which will be graded by modified CTCAE version 3.0 Dermatology Skin Assessment (*Appendix 4*). The investigator is responsible for reviewing laboratory test results and determining whether an abnormal value in an individual study subject represents a change from values before the study. In general, abnormal laboratory findings without clinical significance (based on the investigator's judgment) should not be recorded as adverse events; however, laboratory value changes requiring therapy or adjustment in prior therapy are considered adverse events.

Serious Adverse Events

A serious adverse event (SAE) is defined as an adverse event that:

- Is fatal
- Is life threatening (places the subject at immediate risk of death)
- Requires in-patient hospitalization or prolongation of existing hospitalization
- Results in persistent or significant disability/incapacity
- Is a congenital anomaly/birth defect
- Other significant medical hazard

A hospitalization meeting the regulatory definition for “serious” is any inpatient hospital admission that includes a minimum of an overnight stay in a health care facility. Any adverse event that does not meet one of the definitions of serious (e.g. emergency room visit, outpatient surgery, or requires urgent investigation) may be considered by the investigator to meet the “other significant medical hazard” criterion for classification as a serious adverse event. Examples include allergic bronchospasm, convulsions, and blood dyscrasias.

Hospitalization for the performing of protocol-required procedures or administration of study treatment is not classified as an SAE.

Reporting Procedures for All Adverse Events

All AEs occurring after informed consent signing observed by the investigator or reported by the subject (whether or not attributed to investigational product) will be reported on the case report form. The investigator is responsible for ensuring that all adverse events observed by the investigator or reported by subjects are properly captured in the subjects' medical records.

The following adverse event attributes must be assigned by the investigator:

- Adverse event diagnosis or syndrome(s) (if known, signs or symptoms if not known)
- Event description (with detail appropriate to the event)
- Dates of onset and resolution
- Severity
- Assessment of relatedness to study treatment
- Action taken.

Medically significant adverse events considered related to the investigational product by the investigator or the sponsor will be followed until resolved or considered stable.

It will be left to the investigator's clinical judgment to determine whether an adverse event is related and of sufficient severity to require the subject's removal from treatment or from the study. A subject may also voluntarily withdraw from treatment due to what he or she perceives as an intolerable adverse event. If either of these situations arises, the subject should be strongly encouraged to undergo an end-of-study assessment and be under medical supervision until symptoms cease or the condition becomes stable.

Serious Adverse Events Reporting Procedures

Serious adverse events will be collected and recorded at least throughout the study period, beginning with the signing of the informed consent through 30 days after the end of the treatment phase or through the safety follow-up visit, whichever is longer.

Subsite SAE reporting requirements are located at the end of this section. Subsites are NOT permitted to report directly to the FDA, Amgen, or the OSU IRB.

The investigator should notify the Sponsor ([name], PhD) of all serious adverse events occurring at the site(s) in accordance with FDA Regulations. The Sponsor will medically review all SAEs. The Sponsor will ensure the notification of the appropriate Ethics Committees/Institutional Review Boards, of all serious adverse events occurring at the site(s) in accordance with FDA regulations.

The study sponsor is responsible for providing all suspected serious adverse drug reactions (SADRs) related or possibly related to panitumumab to Amgen within 1 month of the event. It is possible that Amgen may request follow-up information from the sponsor.

All suspected unexpected serious adverse reactions (SUSARs) related or possibly related to panitumumab and their follow-up reports must be reported to Amgen within 1 working day of submission to the FDA, IRB or IEC. A copy of any safety report submitted to the FDA, IRB or IEC, should be faxed to Amgen, within 24 hours of such submission. The sponsor is responsible to ensure that the latest investigator's brochure is used as the source document for determining the expectedness of an SAE.

A copy of any safety report submitted to the FDA, or any other regulatory agency, IRB or IEC, should be faxed with the Amgen Adverse Event fax coversheet to Amgen, within 24 hours of such submission, at:

Amgen Global Safety

[contact]

AND Principle Investigator: [name], PhD

AND The Ohio State University IRB:

REPORTING	FREQUENCY
SADRs	Within 1 month of the event
SUSARs	Within 1 business day of FDA submission

Investigators should not wait to receive additional information to fully document the event before notifying the sponsor of the SAE. Any SAE, if brought to the attention of the investigator at any time after cessation of study drug, and considered by the investigator to be possibly related to study drug, should be reported.

Subsite SAE Reporting Requirements

Subsites are NOT permitted to report directly to the FDA, Amgen, or the OSU IRB. Subsites must notify the OSU PI and OSU Subsite Coordinator of all SAEs within 24 hours of knowledge of the event. All SAEs must be reported on a MedWatch 3500A and submitted with the SAE Submission Form (Appendix 8) to the OSU Subsite Coordinator within 5 business days of knowledge of the event. All subsite SAEs will be reviewed by the OSU PI. Any subsite SAE that requires reporting to the FDA, Amgen, or the OSU IRB will be sent by the OSU Subsite Coordinator. Subsites should report to their IRB of record per their institutional and IRB policies.

